10.6.2 Product Use Patterns

The table of current behavior, CB(i), at MT(i) will provide the information of product use patterns (Table 14.2.2.4.1) for CC smokers cohort. In the IQOS users cohort a similar table (Table 14.2.2.5.1) of CB(i) over IQOS time will be displayed by month of enrollment (i.e. separately for enrollment at 3 months, 6 months, 9 months and 12 months CASI) and overall. Other product use patterns, like uptake of HnB products for CC cohort by CB(i) (Table

Confidentiality Statement

Data and information contained in this document are considered to constitute trade secrets and confidential commercial information, and the legal protections provided to such trade secrets and confidential information are hereby claimed under the provisions of applicable law. No part of this document may be publicly disclosed without the written consent of Philip Morris Products S.A.

14.2.2.6.1), and description of use of HnB and THS Brand products, cigarettes, e-cigarettes, smokeless tobacco pipe, roll-your-own cigarettes, cigars/pipes/kiseru, and chewing tobacco/snus/snuff use for IQOS users (Table 14.2.2.7.1) cohort will be presented.

Uptake of product (not CC) is defined based on the product use questionnaire, as when a participant uses at MT(i) an HnB or THS product and was not using that product at the previous time-point (Table 14.2.2.6.1). Frequency of HnB product and THS brand, cigarettes and e-cigarettes, smokeless tobacco pie, roll-your-own cigarettes, cigars/pipes/kiseru and chewing tobacco/snus/snuff use will also be summarized by each IQOS time-point no matter the participant uses it previously or not (Table 14.2.2.7.1).

Additional product transition table will also be provided between CB(i-1) and CB(i) (Table 14.2.2.8).

The following outputs will be repeated by sex and age group:

- Descriptive Statistics of CB in the CC smokers cohort (Table 14.2.2.4.2 to 14.2.2.4.3)
- Descriptive Statistics of CB in the IQOS users cohort (Table 14.2.2.5.2 to 14.2.2.5.3)
- Descriptive Statistics of Uptake of HnB Products by CB in the CC smokers cohort (Table 14.2.2.6.2 to 14.2.2.6.3)
- Descriptive Statistics of THS and OTP use in the IQOS users cohort (Table 14.2.2.7.2 to 14.2.2.7.3)

A Sankey diagram will display the flow of CB(i) over time for the CC smokers and IQOS users separately (Figures 14.1.2.2.1 and 14.1.2.3.1). Figure 14.1.2.3.1 will include, within the band, the numbers of participants already enrolled or newly enrolled for each IQOS time. Those lost to follow-up will be documented in a band as well. For IQOS users the diagram will be repeated separately for those enrolled at IQOS time 3 months, 6 months, 9 months and 12 months (Figure 14.2.4.1). Figures will be repeated by sex and age-groups (14.1.2.2.2, 14.1.2.2.3, 14.1.2.3.2, 14.1.2.3.3, 14.1.2.4.2, 14.1.2.4.3).

Corresponding information is provided in participant data listings (Listing 14.3.2.4.2).

Confidentiality Statement

Data and information contained in this document are considered to constitute trade secrets and confidential commercial information, and the legal protections provided to such trade secrets and confidential information are hereby claimed under the provisions of applicable law. No part of this document may be publicly disclosed without the written consent of Philip Morris Products S.A.

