**Table 1 Inclusion Criteria**

Inclusion Criteria

1. Adults legally authorized to buy tobacco products in Japan (20 years of age)2. Japanese3. Participant is able to understand the information provided in the informed consent form (ICF)4. Signed ICF5. Willing to participate in the study and has access to the internet6. For IQOS users:
o Is currently using IQOS HeatSticks, ando Has used at least 100 IQOS HeatSticks in their lifetime, ando Has used IQOS HeatSticks for at least 2 months 
NOTE: The use of IQOS HeatSticks defines the user as an IQOS user, regardless of other tobacco or nicotine product use
 
7. For CC smokers:
o Is currently using CC, ando Is not currently using IQOS HeatSticks, ando Has used at least 100 CC in their lifetime

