7.1.1.1 IQOS CASI was missed due to the Study Design

During the first year, IQOS participants may enter the study between 2 and 12 months of product use. All IQOS participants will complete their baseline questionnaire at time of entry (baseline CASI). After the baseline CASI, the next CASI is dependent on the exposure time to IQOS. IQOS participants will not complete a CASI if their baseline CASI is within the timeframe (\pm 4 weeks of the next required CASI).

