7.1.1.2 CASI was missed by Participant

The study participant did not complete a CASI despite being enrolled in the study. For IQOS users during the first year of the study if the Baseline CASI is conducted within the assessment window for a specific CASI, the Baseline will be used in the assessment of the time-point.

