10.6 Planned Statistical Analyses

10.6.1 Product Use Level

To assess objective 1, the following analysis will be conducted.

Summary table of the use of tobacco and nicotine containing products over time for all enrolled participants in the CC cohort at enrollment (Table 14.2.2.1.1). For the IQOS users cohort there will be two summary tables. Table 14.2.2.2.1 will describe product use for each CB at each IQOS time. Table 14.2.3.1 will describe the flow of product use overtime, separately for those who have started the study at IQOS time 3 months, 6 months, 9 months and 12 months and overall (regardless of the IQOS time at enrollment). These tables will summarize:

- Mean number of cigarettes smoked (per day) - CPD(i)
- Mean number of THS Tobacco Sticks used (per day)- THSPD(i)
- Mean number of Heat-not-Burn products used (per day)- HnBPD(i)
- Mean number of other cigarettes product used (per day)- OTPD(i)
- Mean number of e-cigarettes used (per day)- ePD(i)
- Percent of cigarettes used (%CC)
- Percent of THS Tobacco Sticks used (%THS)
- Percent of Heat-not-Burn products used (%HnB)
- Percent of other cigarette products used (%OTP)
- Percent of e-cigarettes used (%e-cig)

All the above tables will be repeated by sex and age group (Tables 14.2.2.1.2, 14.2.2.1.3, 14.2.2.2.2, 14.2.2.2.3, 14.2.2.3.2 and 14.2.2.3.3).

The following figures will be provided at each MT(i).

- Bar chart of mean consumption of CPD(i), THSPD(i), HnBPD(i), OTPD(i), ePD(i), with 95% at each (applicable) IQOS time, separately for participants that entered at CASI 3 months, 6 months, 9 months and 12 months and overall (Figure 14.1.2.1).

Corresponding information is provided in participant data listings (Listing 14.3.2.4.1).

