Table 14.2.2.2.2	Descriptive Statistics of Tobacco and Nicotine Containing Products (THS Users) by Current Behavior, Timepoint and Sex – Enrolled Population
Table 14.2.2.2.3	Descriptive Statistics of Tobacco and Nicotine Containing Products (THS Users) by Current Behavior, Timepoint and Age Group – Enrolled Population
Table 14.2.2.3.1	Descriptive Statistics of Tobacco and Nicotine Containing Products (THS Users) Over time by IQOS Duration at Enrollment and Overall – Enrolled Population
Table 14.2.2.3.2	Descriptive Statistics of Tobacco and Nicotine Containing Products (THS Users) Over Time by IQOS Duration at Enrollment and Overall by Sex – Enrolled Population
Table 14.2.2.3.3	Descriptive Statistics of Tobacco and Nicotine Containing Products (THS Users) Over Time by IQOS Duration at Enrollment and Overall by Age Group – Enrolled Population
Table 14.2.2.4.1	Descriptive Statistics of Current Behavior (CC Smokers) – Enrolled Population
Table 14.2.2.4.2	Descriptive Statistics of Current Behavior (CC Smokers) by Sex – Enrolled Population
Table 14.2.2.4.3	Descriptive Statistics of Current Behavior (CC Smokers) by Age Group – Enrolled Population
Table 14.2.2.5.1	Descriptive Statistics of Current Behavior Over Time (THS Users) by IQOS Duration at Enrollment and Overall – Enrolled Population
Table 14.2.2.5.2	Descriptive Statistics of Current Behavior Over Time (THS Users) by IQOS Duration at Enrollment and Sex – Enrolled Population
Table 14.2.2.5.3	Descriptive Statistics of Current Behavior Over Time (THS Users) by IQOS Duration at Enrollment and Age Group – Enrolled Population
Table 14.2.2.6.1	Descriptive Statistics of Uptake of HnB Products by Current Behavior (CC Smokers) – Enrolled subjects
Table 14.2.2.6.2	Descriptive Statistics of Uptake of HnB Products by Current Behavior and Sex (CC Smokers) – Enrolled Population
Table 14.2.2.6.3	Descriptive Statistics of Uptake of HnB Products by Current Behavior and Age Group (CC Smokers) – Enrolled Population
Table 14.2.2.7.1	Descriptive Statistics of THS and Other Products Use (THS Users) – Enrolled Population
Table 14.2.2.7.2	Descriptive Statistics of THS and Other Products Use by Sex (THS Users) – Enrolled Population
Table 14.2.2.7.3	Descriptive Statistics of THS and Other Products Use by Age Group (THS Users) – Enrolled Population

Confidentiality Statement

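### SAP 3.0 presents Table 14.2.2.7.1 (THS brand and other product use, IQOS cohort) by IQOS time with no entry-month split, so months 6, 9 and 12 mix followed participants with new entrants selected as THS users

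*SAP*

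**What the plan says.** **The table.** SAP 10.6.2 describes Table 14.2.2.7.1 as the frequency of use of each product in the IQOS cohort, which "will also be summarized by each IQOS time-point no matter the participant uses it previously or not (Table 14.2.2.7.1"). In SAP Table 4 it is titled "Descriptive Statistics of THS and Other Products Use (THS Users"). The sex and age repeats, 14.2.2.7.2 and 14.2.2.7.3, add only those factors.

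**Entry and eligibility.** SAP 7.1.1.1: "IQOS participants may enter the study between 2 and 12 months of product use". SAP Table 1 requires of an IQOS user: "Is currently using IQOS HeatSticks".

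**What counts at a time-point.** For IQOS users the measurement time is IQOS time (SAP 7.1.2.4). If the baseline CASI falls in a time-point's window, "the Baseline will be used in the assessment of the time-point" (SAP 7.1.1.2; SAP 10.1.4 item (1)b says the same, with a window of 4 weeks either side). Percentages use everyone with non-missing data (SAP 10.1.2).

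**Related outputs that are split.**
- Table 14.2.2.5.1 is titled "Descriptive Statistics of Current Behavior Over Time (THS Users) by IQOS Duration at Enrollment and Overall", and the text confirms it: "separately for enrollment at 3 months, 6 months, 9 months and 12 months CASI) and overall".
- Table 14.2.2.3.1 (printed as 14.2.3.1 in SAP 10.6.1) has entry-month strata for 3, 6, "9 months and 12 months and overall (regardless of the IQOS time at enrollment").
- Figure 14.1.2.1 is split in the same way. Figure 14.1.2.3.1 shows already enrolled and newly enrolled numbers at each IQOS time.

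**Related outputs that are not split.** Tables 14.2.2.2.x and 14.2.2.8.

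**The concern.** At months 6, 9 and 12 one percentage combines two groups. Participants already under follow-up have had time to stop THS. New entrants are represented by their enrolment CASI, at which current THS use was a condition of joining. The THS-use frequency is then partly a product of the inclusion criteria, and a reader moving along the IQOS-time axis could take it for continued use.

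The table matters because it is the only IQOS-cohort table described as giving user frequencies by THS brand and by detailed product over IQOS time. If those frequencies are blended across entry groups here, no other summary table separates them.

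**Working it through.** **Which time-points are affected.** Month 3 is essentially all entrants. Months 6, 9 and 12 mix both groups. Entry ends at 12 months of use, so months 15 and 18 have no new entrants; only unequal time since entry remains there.

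**Dilution.** Let w be the newly enrolled share of those counted, and q the share of already followed participants with no THS use. With no eligibility violators, new entrants contribute zero, so

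pooled no-THS share = w × 0 + (1 - w) × q = (1 - w) × q.

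This needs no assumption about how participants stop. The direction is fixed for THS: pooling lowers the no-THS share. For other products the entrants' value is not fixed, so the direction is unknown.

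**Inputs for an illustration.** The plan states no figure for this effect, so there is none to reproduce. It gives neither w nor a THS stopping rate. The nearest rate is in Protocol 12.2.3: at most 20% per year changing to another behavior. With the 5% drop-out assumed there, 500 × (1 - 0.05 - 0.20) = 375, the first entry of the protocol's person-time table, so the 20% is read as the protocol uses it. It covers any behavior change, so I treat it as an upper illustration for stopping THS.

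**Assumptions.** Share stopped after m months = 1 - 0.80^(m/12), with no return to THS and no drop-out. This gives 5.43%, 10.56% and 15.41% after 3, 6 and 9 months. Three entry patterns:

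- *Uniform over 2 to 12 months*, with a window of 4 weeks = 0.92 month. At month 6, w = 1.84/4.92 = 37.4%; at month 9, 1.84/7.92 = 23.2%; at month 12, 0.92/10 = 9.2%.
- *Equal numbers exactly at months 3, 6, 9 and 12.* At month 12: followed = (5.43 + 10.56 + 15.41)/3 = 10.46; pooled = 0.75 × 10.46 = 7.85.
- *Late-loaded, 1:2:3:4 at those months.* At month 12: followed = (1 × 15.41 + 2 × 10.56 + 3 × 5.43)/6 = 8.80; pooled = 0.60 × 8.80 = 5.28.

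| Entry pattern | Month | w | Followed, no THS (%) | Pooled (%) | Gap (points) |
|---|---|---|---|---|---|
| Uniform | 6 | 37.4% | 4.46 | 2.79 | 1.7 |
| | 9 | 23.2% | 7.05 | 5.41 | 1.6 |
| | 12 | 9.2% | 9.55 | 8.67 | 0.9 |
| Equal, exact months | 6 | 50% | 5.43 | 2.71 | 2.7 |
| | 9 | 33.3% | 7.99 | 5.33 | 2.7 |
| | 12 | 25% | 10.46 | 7.85 | 2.6 |
| Late-loaded | 6 | 66.7% | 5.43 | 1.81 | 3.6 |
| | 9 | 50% | 7.14 | 3.57 | 3.6 |
| | 12 | 40% | 8.80 | 5.28 | 3.5 |

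**Sensitivity.**
- Early-loaded 4:3:2:1 entry at month 12: w = 10%, 11.6 followed against 10.4 pooled.
- At 10% per year, month 12: 4.7 against 4.2 (uniform) and 5.1 against 3.8 (exact months).
- At 5% per year, month 12: 2.3 against 2.1 and 2.5 against 1.9.
- Adding 5% annual drop-out to the equal exact-month case leaves the gaps at 2.6 to 2.7 points.

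**The case against.** **The table is cross-sectional by design.** It reports use at each time-point and is not offered as retention. That stands, but its wording on earlier use concerns whether the participant used the product before. It says nothing about when the participant entered the study.

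**Other outputs cover part of the ground.** Table 14.2.1.2.1 gives behavior groups by CASI at entry (SAP 10.2). Table 14.2.1.6.2 compares participants who stopped IQOS with those who continued (SAP 10.3). Table 14.2.2.3.1 gives means and percent consumption for the main product groups by entry month. The newly enrolled counts in Figure 14.1.2.3.1 let a reader roughly undo the dilution for overall THS use, by dividing by (1 - w). All of this stands. What it leaves uncovered is user frequency at brand and detailed-product level by IQOS time; for that a reader would have to rebuild the table from the listings.

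**Entry may have been early.** Protocol 9.2 defines wave 1, the only wave analyzed, as users who started IQOS within 6 months before launch. Fast enrolment would load entry early and shrink w at months 9 and 12. Enrolment pace is not given, so this cannot be settled.

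**Layout is not final.** Detailed layouts sit in TLF shells that were not available, and SAP 3 lets titles change without an amendment. A split or footnote may already exist there.

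**Stronger readings that the documents do not support.**
- A reader might infer that the SAP overlooks staggered entry in the IQOS cohort. It does not: Tables 14.2.2.3.x and 14.2.2.5.x and Figure 14.1.2.1 are split.
- A reader might infer the reverse, that every related table is split and lacks only a label on its pooled column. Tables 14.2.2.2.x and 14.2.2.8 have no split, and the pooled column of 14.2.2.3.1 is already described as ignoring entry time.
- A reader might take new entrants' no-THS share as exactly zero. All analyses use the enrolled population (SAP 9.1), and SAP 9.2.1 states no exclusion for eligibility violations, so the share is zero only if there are none.

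**Conclusion.** The point holds for Table 14.2.2.7.1 and its sex and age repeats. As the SAP text and Table 4 describe them, the rows for months 6, 9 and 12 pool followed participants with entrants who, barring eligibility violations, are THS users by inclusion. THS-use frequency is raised by a known mechanism in a known direction.

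Its size is unknown. The illustrated gap of about 1 to 3 points with even entry, and up to 3.6 points with late-loaded entry, rests on an assumed entry pattern and on using the protocol's 20% maximum as if it were a stopping rate.

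Severity is minor: the analysis is descriptive, limited to wave 1, and cessation is not assessed. Confidence is high on the mechanism and moderate on the final layout.

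**What to change.** In SAP 10.6.2 and Table 4, present Table 14.2.2.7.1 by IQOS duration at enrolment (3, 6, 9 and 12 months) and overall, as Table 14.2.2.5.1 is. Handle the sex and age repeats as Tables 14.2.2.5.2 and 14.2.2.5.3 are.

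The cost is SAP wording and programming, with no new data. The entry-month variable is already needed for Tables 14.2.2.3.x and 14.2.2.5.x. The downside is longer tables with some small cells: at the planned 500 IQOS users per wave, an equal split gives 500/4 = 125 per entry month before missed CASIs, and fewer given the recruitment problems that SAP 3 reports. SAP 10.1.4.1 already limits what is shown for categories with fewer than 4 subjects.

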11 ANALYSES AND REPORTING

11.1 Interim Analyses and Data Monitoring

Not applicable due to study termination (details in Section 8).

11.2 Safety Reporting

Not applicable.

11.3 Topline Results

Not applicable.

11.4 Final Analyses

The list of all tables, figures and listings to be presented at final analysis are presented in Table 4 below.

Confidentiality Statement

Data and information contained in this document are considered to constitute trade secrets and confidential commercial information, and the legal protections provided to such trade secrets and confidential information are hereby claimed under the provisions of applicable law. No part of this document may be publicly disclosed without the written consent of Philip Morris Products S.A.

**Table 4 List of Results Produced at Final Analysis**

TLF no	Title
TABLES	
Table 14.2.1.1.1	Subject Attendance by Cohort– Enrolled Population
Table 14.2.1.1.2	Subject Attendance by Cohort and Sex – Enrolled Population
Table 14.2.1.1.3	Subject Attendance by Cohort and Age Group – Enrolled Population
Table 14.2.1.2.1	Distribution of Behavior Groups in the THS Users Cohort at Enrollment – Enrolled Population
Table 14.2.1.2.2	Distribution of Behavior Groups in the THS Users Cohort at Enrollment by Sex – Enrolled Population
Table 14.2.1.2.3	Distribution of Behavior Groups in the THS Users Cohort at Enrollment by Age Group – Enrolled Population
Table 14.2.1.3	Protocol Deviations – Enrolled Population
Table 14.2.1.4.1	Demographics and Baseline Characteristics at Enrollment– Enrolled Population
Table 14.2.1.4.2	Demographics and Baseline Characteristics by Initial Behavior – Enrolled Population
Table 14.2.1.5.1	Descriptive Statistics of Socio-Economic Status Questionnaire – Enrolled Population
Table 14.2.1.5.2	Descriptive Statistics of Socio-Economic Status Questionnaire by Initial Behavior – Enrolled Population
Table 14.2.1.6.1	Characteristics of Participants that Started THS after Enrollment – Enrolled Population
Table 14.2.1.6.2	Characteristics of Participants that Stopped THS after Enrollment – Enrolled Population
Table 14.2.1.6.3	Characteristics of Participants that Stopped all Tobacco Products after Enrollment – Enrolled Population
Table 14.2.2.1.1	Descriptive Statistics of Tobacco and Nicotine Containing Products (CC Smokers) at Enrollment – Enrolled Population
Table 14.2.2.1.2	Descriptive Statistics of Tobacco and Nicotine Containing Products (CC Smokers) at Enrollment by Sex – Enrolled Population
Table 14.2.2.1.3	Descriptive Statistics of Tobacco and Nicotine Containing Products (CC Smokers) at Enrollment by Age Group – Enrolled Population
Table 14.2.2.2.1	Descriptive Statistics of Tobacco and Nicotine Containing Products (THS Users) by Current Behavior and Timepoint – Enrolled Population

Confidentiality Statement

Data and information contained in this document are considered to constitute trade secrets and confidential commercial information, and the legal protections provided to such trade secrets and confidential information are hereby claimed under the provisions of applicable law. No part of this document may be publicly disclosed without the written consent of Philip Morris Products S.A.

Table 14.2.2.2.2	Descriptive Statistics of Tobacco and Nicotine Containing Products (THS Users) by Current Behavior, Timepoint and Sex – Enrolled Population
Table 14.2.2.2.3	Descriptive Statistics of Tobacco and Nicotine Containing Products (THS Users) by Current Behavior, Timepoint and Age Group – Enrolled Population
Table 14.2.2.3.1	Descriptive Statistics of Tobacco and Nicotine Containing Products (THS Users) Over time by IQOS Duration at Enrollment and Overall – Enrolled Population
Table 14.2.2.3.2	Descriptive Statistics of Tobacco and Nicotine Containing Products (THS Users) Over Time by IQOS Duration at Enrollment and Overall by Sex – Enrolled Population
Table 14.2.2.3.3	Descriptive Statistics of Tobacco and Nicotine Containing Products (THS Users) Over Time by IQOS Duration at Enrollment and Overall by Age Group – Enrolled Population
Table 14.2.2.4.1	Descriptive Statistics of Current Behavior (CC Smokers) – Enrolled Population
Table 14.2.2.4.2	Descriptive Statistics of Current Behavior (CC Smokers) by Sex – Enrolled Population
Table 14.2.2.4.3	Descriptive Statistics of Current Behavior (CC Smokers) by Age Group – Enrolled Population
Table 14.2.2.5.1	Descriptive Statistics of Current Behavior Over Time (THS Users) by IQOS Duration at Enrollment and Overall – Enrolled Population
Table 14.2.2.5.2	Descriptive Statistics of Current Behavior Over Time (THS Users) by IQOS Duration at Enrollment and Sex – Enrolled Population
Table 14.2.2.5.3	Descriptive Statistics of Current Behavior Over Time (THS Users) by IQOS Duration at Enrollment and Age Group – Enrolled Population
Table 14.2.2.6.1	Descriptive Statistics of Uptake of HnB Products by Current Behavior (CC Smokers) – Enrolled subjects
Table 14.2.2.6.2	Descriptive Statistics of Uptake of HnB Products by Current Behavior and Sex (CC Smokers) – Enrolled Population
Table 14.2.2.6.3	Descriptive Statistics of Uptake of HnB Products by Current Behavior and Age Group (CC Smokers) – Enrolled Population
Table 14.2.2.7.1	Descriptive Statistics of THS and Other Products Use (THS Users) – Enrolled Population
Table 14.2.2.7.2	Descriptive Statistics of THS and Other Products Use by Sex (THS Users) – Enrolled Population
Table 14.2.2.7.3	Descriptive Statistics of THS and Other Products Use by Age Group (THS Users) – Enrolled Population

Confidentiality Statement

Data and information contained in this document are considered to constitute trade secrets and confidential commercial information, and the legal protections provided to such trade secrets and confidential information are hereby claimed under the provisions of applicable law. No part of this document may be publicly disclosed without the written consent of Philip Morris Products S.A.

Table 14.2.2.8	Descriptive Statistics of Transitions at each Timepoint – Enrolled Population
----------------	---

FIGURES

Figure 14.1.2.1 Use of Tobacco and Nicotine Containing Products (THS Users) Over Time by IQOS Duration at Enrollment and Overall – Enrolled Population

Figure 14.1.2.2.1 Behavior Flow Over Time (CC Smokers) – Enrolled Population

Figure 14.1.2.2.2 Behavior Flow Over Time (CC Smokers) by Sex – Enrolled Population

Figure 14.1.2.2.3 Behavior Flow Over Time (CC Smokers) by Age Group – Enrolled Population

Figure 14.1.2.3.1 Behavior Flow Over Time (THS Users) – Enrolled Population

Figure 14.1.2.3.2 Behavior Flow Over Time (THS Users) by Sex – Enrolled Population

Figure 14.1.2.3.3 Behavior Flow Over Time (THS Users) by Age Group – Enrolled Population

Figure 14.1.2.4.1 Behavior Flow Over Time (THS Users) – Enrolled Population

Figure 14.1.2.4.2 Behavior Flow Over Time (THS Users) by Sex – Enrolled Population

Figure 14.1.2.4.3 Behavior Flow Over Time (THS Users) by Age Group – Enrolled Population

LISTINGS

Listing 14.3.1.1 Informed Consent

Listing 14.3.1.2 Participant Disposition

Listing 14.3.1.3 Visit Dates

Listing 14.3.2 Protocol Deviations

Listing 14.3.2.3.1 Demographics at Enrollment

Listing 14.3.2.3.2 SES Questionnaire

Listing 14.3.2.3.3 Smoking History

Listing 14.3.2.4.1 Product Use

Listing 14.3.2.4.2 Current Behavior and Tobacco/Nicotine Containing Products Average Consumption

LISTINGS [REDACTED]

Listing 14.3.2.1.1 Informed Consent

Listing 14.3.2.1.2 Participant Disposition

Listing 14.3.2.1.3 Visit Dates

Listing 14.3.2.2 Protocol Deviations

Listing 14.3.2.2.3.1 Participant of Each Wave

Listing 14.3.2.2.3.2 Participant Analysis Sets

Listing 14.3.2.2.4.1 Demographics

Listing 14.3.2.2.4.2 SES Questionnaire

Listing 14.3.2.2.4.3 Smoking History/core questionnaires

Confidentiality Statement

Data and information contained in this document are considered to constitute trade secrets and confidential commercial information, and the legal protections provided to such trade secrets and confidential information are hereby claimed under the provisions of applicable law. No part of this document may be publicly disclosed without the written consent of Philip Morris Products S.A.

Listing 14.3.2.2.6.1	Product Use
Listing 14.3.2.2.6.2	Current Behavior and Tobacco/Nicotine Containing Products Average Consumption
Listing 14.3.2.2.6.3	Current Event
Listing 14.3.2.2.6.4	Intention to Stop Questionnaire
Listing 14.3.2.2.6.5	Smoking Urges-brief (QSU-b)
Listing 14.3.2.2.6.6	Total and Factor Score of Smoking Urges-brief (QSU-b)
Listing 14.3.2.2.6.7	Modified Cigarette Evaluation Questionnaire (MCEQ)
Listing 14.3.2.2.6.8	Subscale Scores from Modified Cigarette Evaluation Questionnaire (MCEQ)
Listing 14.3.2.2.6.9	Self-Reported Changes Questionnaire (SRCQ)
Listing 14.3.2.2.6.10	Perception of Risk Associated with Using CCs
Listing 14.3.2.2.6.11	Perception of Risk Associated with Using MRTPs
Listing 14.3.2.2.6.12	Perception of Risk Associated with Using NRTs
Listing 14.3.2.2.6.13	Perception of Risk Associated with Using ENDs
Listing 14.3.2.2.6.14	Subscale Scores from Perception of Risk Associated with Using CCs
Listing 14.3.2.2.6.15	Subscale Scores from Perception of Risk Associated with Using MRTPs
Listing 14.3.2.2.6.16	Subscale Scores from Perception of Risk Associated with Using NRTs
Listing 14.3.2.2.6.17	Subscale Scores from Perception of Risk Associated with Using ENDs
Listing 14.3.2.2.6.18	Fagerström Test for Nicotine Dependence (FTND) Questionnaire
Listing 14.3.2.2.6.19	Total Score of Fagerström Test for Nicotine Dependence (FTND) Questionnaire
Listing 14.3.2.2.6.20	Health Outcome Questionnaire
Listing 14.3.2.2.6.21	Cough Assessment
Listing 14.3.2.2.6.22	Lifestyle Assessment
Listing 14.3.2.2.8.1.1	Clinical Risk Endpoints (CREs) Values Associated with Cardiovascular Disease
Listing 14.3.2.2.8.1.2	Clinical Risk Endpoints (CREs) Values Associated with Respiratory Disease
Listing 14.3.2.2.8.2	Vital Signs

*These listings will be produced on SDTM data only. Derived variables will not be presented.

